5. INTRODUCTION

5.1. Background

Hereditary angioedema (HAE) with C1 esterase inhibitor (C1-INH) deficiency is an autosomal dominant disorder characterized by recurrent episodes of swelling of the skin, pharynx, larynx, gastrointestinal tract (GI), genitals, and extremities (Longhurst and Cicardi 2012). The frequency of attacks varies, from rarely in some patients to every few days in others. Angioedema attacks may or may not be precipitated by a stimulus (such as stress, trauma, or estrogen) and are typically rapid in onset, with symptoms subsiding gradually over the following 3 to 5 days (Zuraw and Christiansen 2011). Oropharyngeal swelling can be life-threatening (Bork, Hardt et al. 2012), while attacks in other sites, including limbs, genitalia, face, and intestines, can be painful, disabling, and disfiguring and have a significant impact on functionality and quality of life (QoL) (Lumry, Castaldo et al. 2010). Although mortality risk from asphyxiation is much higher in undiagnosed patients with HAE, deaths still occur in diagnosed patients with access to care at centers of excellence (Bork, Hardt et al. 2012).

Extensive evidence from animal models and clinical studies supports the role of bradykinin (BK) as the principal mediator of the signs and symptoms that characterize attacks of HAE (Han, MacFarlane et al. 2002, Kaplan 2010, Zuraw and Christiansen 2011). Plasma kallikrein is a serine protease integral to the contact activation pathway (Saxena, Thompson et al. 2011). Kallikrein circulates in plasma as a zymogen, prekallikrein (PKK), bound to one of its main substrates, high-molecular-weight kininogen (HK). During contact activation, PKK is cleaved by activated factor XII, forming the active protease kallikrein. Kallikrein in turn cleaves HK, producing BK (Kaplan and Ghebrehiwet 2010). The activation of the BK B₂ receptor by BK ultimately results in vasodilatation, increased vascular permeability, and contraction of smooth muscle, all of which lead to the tissue swelling that characterizes HAE (Kaplan 2010).

BCX7353 (berotralstat) is a potent, synthetic small molecule inhibitor of plasma kallikrein. In contrast to parenterally administered options commercially available for prophylaxis against HAE attacks, inhibition of kallikrein with an orally bioavailable small molecule such as BCX7353 offers the advantage of oral administration.

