5.4. Rationale for Study

The genetic and clinical features of HAE in Japan mirror Western patients (Yamamoto, Horiuchi et al. 2012). Currently, the only treatment approved for prevention of angioedema attacks in Japan is Berinert, a C1-INH concentrate, which is approved for the treatment of acute episodes and pre-procedure prevention (short-term prophylaxis) of acute episodes of HAE. Therefore, androgens and medications with limited, if any, effectiveness such as tranexamic acid and antihistamines are often used as prophylaxis in Japan (Ohsawa, Honda et al. 2015). Berinert must be administered by a healthcare professional. Icatibant (BK B₂ receptor antagonist) and Berinert have been approved for HAE treatment in Japan.

A survey of Japanese physicians who treat patients with HAE revealed that time to diagnosis is long and licensed treatment options for HAE are underused (Ohsawa, Honda et al. 2015). Ten percent of patients had attacks that required airway management (emergency intubation or tracheotomy), 3% of patients underwent abdominal surgery with an uncertain diagnosis, 21% of patients required hospitalization, 8% of patients had at least 20 HAE attacks per year, and 12% of patients reported the death of a relative due to HAE (Ohsawa, Honda et al. 2015). In Japan, there remains a significant medical need to provide additional HAE treatment options that are efficacious, convenient, and well tolerated, especially given the lack of effective treatments for the prevention of attacks in Japan (Ohsawa, Honda et al. 2015).

BCX7353 is an oral kallikrein inhibitor in development for prevention of angioedema attacks in patients with HAE Type 1 and 2. BCX7353 has activity against plasma kallikrein at low nanomolar concentrations (Section 5.2) that are attainable and sustained in humans following oral administration. In both the randomized, double-blind, placebo-controlled, Phase 3 study (BCX7353-302) and the proof-of-concept, 28-day, placebo-controlled, Phase 2 study (BCX7353-203), the rate of angioedema attacks in subjects randomized to BCX7353 was statistically significantly lower than in placebo subjects and BCX7353 was generally safe and well tolerated. These data support further clinical development of BCX7353 as a potential future option for the prevention of HAE attacks in patients around the world.

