11.4.2.1. Confirmation of Angioedema Events

Subjects will continue to document all angioedema events that occur in their e-diary throughout Part 3. Investigator follow-up of angioedema events and expert confirmation of events will not be required for Part 3. All angioedema events recorded by the subjects will be reviewed and confirmed or rejected according to a set of pre-defined rules prior to inclusion in effectiveness analyses. These rules will be outlined in the SAP.

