12.1.1. Definitions

12.1.1.1. Adverse Event

An AE is any untoward medical occurrence in a clinical study subject. No causal relationship with the study drug or with the clinical study itself is implied. An AE may be an unfavorable and unintended sign, symptom, syndrome, or illness that develops or worsens during the clinical study. Clinically relevant abnormal results of diagnostic procedures including abnormal laboratory findings (eg, requiring unscheduled diagnostic procedures or treatment measures, or resulting in withdrawal from the study) are considered to be AEs. If the diagnostic procedure prompts no additional treatment, visits, or monitoring, it will not meet the definition of an adverse event.

This includes the following:

- AEs not previously observed in the subject that emerge during the protocol-specified AE reporting period (see Section 12.1.2), including medical triggers resulting in an angioedema event. Emotional stress will not be considered an AE unless it results in a medical diagnosis or requires medical treatment.
- Findings from protocol-mandated interventions. This can include laboratory assessments performed in the course of the clinical trial. AEs should be reported only if the abnormalities are changes from baseline and are clinically significant as described above.
- Pre-existing medical conditions (other than the condition being studied) judged by the investigator to have worsened in severity or frequency or changed in character during the protocol-specified AE reporting period. When recording such events on an AE/SAE eCRF page, it is important to convey the concept that the preexisting condition has changed by including applicable descriptors (eg, "more frequent headaches").

An adverse reaction is defined in Article 2(n) of Directive 2001/20/EC as follows: all untoward and unintended responses to a study drug/IMP related to any dose administered. The definition covers also medication errors and uses outside what is foreseen in the protocol, including misuse and abuse of the product. The definition implies a reasonable possibility of a causal relationship between the event and the study drug/IMP. This means that there are facts (evidence) or arguments to suggest a causal relationship.

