For the purposes of this protocol, angioedema events and their associated symptoms will not be defined as AEs, even if the subject requires hospitalization. This information, as well as all HAE attacks and associated symptoms, are reported in the subject's e-diary and is a reflection of the disease under study. The events that may trigger an angioedema event such as an infection or trauma are considered AEs and should be reported as such.

Hospitalization scenarios do not require reporting as an SAE where there is no occurrence of an AE. These scenarios include a planned hospitalization or prolonged hospitalization to:

- Perform a routine control screening for a preexisting illness or to diagnose a suspected illness. In the case of the latter, the symptomatology should be reported as an AE and amended if a diagnosis is confirmed.
- Undergo a diagnostic or elective surgical procedure for a preexisting medical condition that has not changed (eg, a joint replacement for which the subject was on a waiting list).
- Undergo medical observation due to HAE (eg, admission after routine dental procedure in an HAE patient).
- Undergo medical observation without the occurrence of an AE due to standard of care in the region or hospital.

Surgical procedures should not be reported as AEs. The condition for which the surgery is required should be reported as the AE, if it occurs or is detected during the study period. Planned surgical measures permitted by the clinical study protocol and the conditions(s) leading to these measures are not AEs, if the condition(s) was (were) known before the start of study treatment. In the latter case the condition should be reported as medical history.

AEs are designated as “nonserious” or “serious.”

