12.1.1.2. Serious Adverse Event

A SAE is an adverse event/reaction that results in any of the following outcomes:

- Death
- Is life-threatening (subject is at immediate risk of death at the time of the event; it does not refer to an event that hypothetically might have caused death if it were more severe)
- Requires subject hospitalization (formal admission to a hospital for medical reasons) or prolongation of existing hospitalization
- Results in persistent or significant disability/incapacity (ie, there is a substantial disruption of a person's ability to carry out normal life functions)

- Is a congenital anomaly/birth defect

Important medical events that may not result in death, are not life-threatening, or do not require hospitalization may be considered a SAE when, based upon appropriate medical judgment, they may jeopardize the subject's health or may require medical or surgical intervention to prevent one of the outcomes listed in this definition. For this study, examples of such events may include allergic bronchospasm requiring intensive treatment in an emergency room or at home, blood dyscrasias, or convulsions that do not result in subject hospitalization.

In addition, the sponsor considers events of abortion (spontaneous or induced), fetal demise, and still birth as SAEs for reporting purposes.

Some hospitalization scenarios, as outlined in Section 12.1.1.1, do not require reporting as SAEs.

Overdose (> 1 dose per calendar day) will be considered an SAE only if any of the seriousness criteria are met. Any clinical complication in association with the overdose should be reported as an AE or SAE (as applicable) along with the overdose (see Section 12.2.3). Details of signs or symptoms, clinical management, and outcome should be reported, if available. Overdose without associated signs or symptoms should not be recorded as AEs but should be recorded as protocol deviations.

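### The exemption of angioedema events from AE reporting makes no exception for fatal or life-threatening attacks, leaving them no required 24-hour report to the sponsor and no place in the TESAE or fatal-SAE outputs

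*Protocol*

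**What the plan says.** Protocol 12.1.1.1 removes angioedema events from the AE definition: "For the purposes of this protocol, angioedema events and their associated symptoms will not be defined as AEs, even if the subject requires hospitalization". It sends them to another record, saying that they "are reported in the subject's e-diary and is a reflection of the disease under study". The same section lets a worsened prior condition count as an AE but excludes the disease under study: "Pre-existing medical conditions (other than the condition being studied) judged by the investigator to have worsened in severity or frequency". Medical triggers of an attack, such as an infection or trauma, remain AEs. Admission for observation because of HAE is listed among hospitalizations that need no SAE report.

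Protocol 12.1.1.2 opens its definition with "A SAE is an adverse event/reaction that results in any of the following outcomes", and death and threat to life are listed as outcomes separate from hospitalization. Sections 12.1.2 and 12.1.5 attach the 24-hour duty to SAEs. Section 12.1.1.3 limits events of special interest to drug-related maculopapular rash.

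On the underlying risk, protocol 5.1 says "Oropharyngeal swelling can be life-threatening" and notes that diagnosed patients still die of the disease.

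For Part 3, protocol 11.4.2.1 says "Investigator follow-up of angioedema events and expert confirmation of events will not be required for Part 3".

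**The concern.** Keeping ordinary attacks out of AE reporting is sensible, because they are the primary efficacy outcome. The difficulty is that the exemption has no upper limit. The one degree of severity it mentions, hospitalization, falls inside it. Read with the SAE definition, it appears to take the gravest outcome of the disease out of expedited reporting.

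Two things are at stake. One is oversight: the trial has a 24-week placebo arm and does not allow prophylaxis to be started, so prompt sponsor knowledge of a fatal or airway-threatening attack matters. The other is the safety result: the proportion with a TESAE is a primary endpoint of Parts 2 and 3, and a reader of those tables would expect deaths and life-threatening events to be in them.

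The plan is also uneven. Under 12.1.5.1 a related maculopapular rash of any severity must reach the sponsor within 24 hours of the investigator's assessment, and an infection that triggers an attack is an AE. A fatal laryngeal attack, as written, is neither.

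**Working it through.** No arithmetic applies; the check is to follow a fatal or life-threatening attack through the definitions and outputs.

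1. **Is it an AE?** No. Protocol 12.1.1.1 excludes angioedema events and their symptoms.
2. **Does it qualify as worsening of a prior condition?** No. That route excludes the condition being studied.
3. **Is it an SAE?** Not by the AE route. Under 12.1.1.2 the serious outcome must belong to an adverse event or reaction. Two openings remain: an attack judged to be an untoward response to study drug may qualify as a reaction, and a serious trigger may be an SAE in its own right.
4. **Is it an event of special interest?** No. Section 12.1.1.3 covers only drug-related maculopapular rash.
5. **Is there a 24-hour duty to the sponsor?** Sections 12.1.2, 12.1.5 and 12.1.5.1 tie it to SAEs and events of special interest. Apart from the openings in step 3, none arises.
6. **Which safety outputs would show it?** The SAP draws its TESAE tables (10.1.1; Tables 14.3.1.4 and 14.3.1.4.ES) and its fatal SAE listing (16.2.7.5 and 16.2.7.5.ES) from AE data, so it would not appear there.
7. **Is there an exception elsewhere?** A search of both documents found none for fatal or life-threatening attacks.

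What would still record the attack:

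| Route | Where | Limit |
|---|---|---|
| e-diary | Protocol 11.4 | Completed by the subject; staff may make no entries |
| Site notification and contact, screening to end of Part 2 | Protocol 11.4.1.1 | Goes to source records and the independent expert; no duty to notify the sponsor's medical monitor |
| Part 3 telephone contacts and visits | Protocol 11.4.2.2, 10.3.5.1 | Periodic; no follow-up of individual attacks required |
| Confirmed event in the eCRF without a diary entry | SAP 6.7.5.1 | Counted in the event rate |
| Event characteristics, including laryngeal status and care sought | SAP 8.8.3; Tables 14.2.10.1 and 14.2.10.1.ES | Efficacy output |
| Listing of confirmed laryngeal events | SAP listing 16.2.6.1.12 | Part 1 only |
| Disposition | SAP 7.1 | Would show a withdrawal, not an SAE |

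So the attack leaves a trace, but no route in the table creates an expedited duty to the sponsor or puts the event in a TESAE output.

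**The case against.** The strongest reply is that the protocol is silent rather than wrong. The exemption mentions hospitalization and stops there, while the SAE criteria list death and threat to life separately, so an investigator could read the exemption as going no further than hospitalization and report a death anyway. That reading is possible, and it means one cannot say such an attack would never be reported. It does not remove the gap: the exempting clause covers angioedema events in general, and hospitalization is given as an example of how far it extends, not as its boundary.

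A second reply is that unseen documents may cover the point. Protocol 12.1.5 refers to a Safety and Medical Management Plan for Japan-specific rules, and 12.3 to a DMC charter. Either could add a requirement. That is why a claim that the DMC would be kept unaware is not supported; what it receives cannot be determined here. But the exemption is stated for this protocol, and sites should not have to find its limit elsewhere.

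Three further inferences should be resisted:

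- **That notification slips from 24 hours to about 2 business days.** These are different clocks. The first runs from the investigator's knowledge to the sponsor; the second is site contact with the subject after the attack ends. The gap is that no sponsor notification is specified at all.
- **That the trial could report no deaths when one had occurred.** Disposition and event records would show something. What would be missing is the SAE entry.
- **That one case in an arm of 8 (1/8 = 12.5 percentage points) measures the harm.** It is only one subject's weight. In the SAP's pooled columns that weight would be about 1/12 = 8.3 points for each dose (8 + 4 subjects) or 1/24 = 4.2 points for all active.

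Finally, counting attacks as TESAEs mixes an efficacy outcome into a safety endpoint. That is fair, and the fix handles it by presenting both counts.

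**Conclusion.** The point stands as a defect in a stated rule, not as a missing detail. The AE exemption, the SAE definition and the risk named in protocol 5.1 do not fit together for fatal or life-threatening attacks. The consequences are limited to two: no required 24-hour report to the sponsor, and no entry in the TESAE tables or the fatal SAE listing. The position is weakest in Part 3, where investigator follow-up of attacks is not required and safety is the primary objective.

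The size cannot be expressed as an expected number of events. The Japanese physician survey cited in protocol 5.4 (10% of patients with attacks needing airway management, 21% needing hospitalization, 12% reporting a relative's death from HAE) shows that the outcome is real in this population, but these are not rates over trial follow-up.

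The conclusion assumes that the attack is not attributed to study drug as a reaction, that no separate trigger AE brings it in, and that the documents not available here add no rule.

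**What to change.** Limit the exemption in protocol 12.1.1.1 so that an angioedema event meeting the existing 12.1.1.2 criteria of death or life-threatening is reported under 12.1.5 within 24 hours of the investigator's awareness, in all three parts and in addition to the e-diary. Align the clause excluding the studied condition from the worsening rule, so that 5.1, 12.1.1.1 and 12.1.1.2 agree. If the Safety and Medical Management Plan already has such a rule, bring it into the protocol.

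In the data and the SAP: flag these events on the SAE eCRF, show TESAEs with and without them, and include them in the fatal SAE listing where they apply. Add them to the DMC data if the charter does not already do so.

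The cost is a short protocol amendment, a flag on an existing form, an extra row in the TESAE tables and possibly a change to the DMC package. The small downside is that a few disease-related events enter one version of the TESAE count. The primary efficacy endpoint and all treatment rules stay as they are.

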12.1.1.2. Serious Adverse Event

A SAE is an adverse event/reaction that results in any of the following outcomes:

- Death
- Is life-threatening (subject is at immediate risk of death at the time of the event; it does not refer to an event that hypothetically might have caused death if it were more severe)
- Requires subject hospitalization (formal admission to a hospital for medical reasons) or prolongation of existing hospitalization
- Results in persistent or significant disability/incapacity (ie, there is a substantial disruption of a person's ability to carry out normal life functions)

- Is a congenital anomaly/birth defect

Important medical events that may not result in death, are not life-threatening, or do not require hospitalization may be considered a SAE when, based upon appropriate medical judgment, they may jeopardize the subject's health or may require medical or surgical intervention to prevent one of the outcomes listed in this definition. For this study, examples of such events may include allergic bronchospasm requiring intensive treatment in an emergency room or at home, blood dyscrasias, or convulsions that do not result in subject hospitalization.

In addition, the sponsor considers events of abortion (spontaneous or induced), fetal demise, and still birth as SAEs for reporting purposes.

Some hospitalization scenarios, as outlined in Section 12.1.1.1, do not require reporting as SAEs.

Overdose (> 1 dose per calendar day) will be considered an SAE only if any of the seriousness criteria are met. Any clinical complication in association with the overdose should be reported as an AE or SAE (as applicable) along with the overdose (see Section 12.2.3). Details of signs or symptoms, clinical management, and outcome should be reported, if available. Overdose without associated signs or symptoms should not be recorded as AEs but should be recorded as protocol deviations.

12.1.1.3. Adverse Events of Special Interest

For this protocol, treatment-emergent maculopapular rashes that are deemed related to BCX7353 will be considered EOSIs. This does not include other types of rashes, such as urticaria or eczema. All treatment-emergent skin conditions should be reported as AEs but only maculopapular rashes deemed related to BCX7353 should be considered EOSIs.

An EOSI event in and of itself will not be considered serious unless it meets the seriousness criteria above. Events of maculopapular rash assessed as possibly, probably, or definitely related to BCX7353 regardless of severity must be reported to the sponsor medical monitor as described in Section 12.1.5.1. Management of BCX7353 drug-related rash is provided in Section 12.2.1.

12.1.2. Method, Frequency, and Time Period for Detecting Adverse Events and Reporting Serious Adverse Events

Reports of all AEs and SAEs, regardless of investigator attribution, are to be collected from the time of signing of the informed consent through to the last study visit (ie, through the posttreatment follow-up visit). All AEs and SAEs are to be reported in the AE eCRF.

AEs should be documented in the eCRF as investigators become aware of them. AEs are to be followed until the event resolves, as follows. If an event is ongoing at the last follow-up visit, Grade 1 and 2 events do not need to be followed if the event is deemed unlikely to be related or not related to study drug (see Section 12.1.3 for AE grading). For all Grade 3 and 4 events or events deemed at least possibly related to use of study drug, the event should be followed until the AE is resolved or the subject is in a clinically stable condition with regards to the AE.

The investigator shall report all SAEs immediately to the sponsor by communicating with the medical monitor (phone or email) and by entering the event into the AE eCRF and by completion of the SAE eCRF within 24 hours of their knowledge of the event (see Section 12.1.5). The SAE eCRF form is an additional form to the AE eCRF that provides important details on the SAE.

The investigator should follow all unresolved SAEs observed during the study until they are resolved, or are judged medically stable, or are otherwise medically explained.

The investigator should attempt, if possible, to establish a diagnosis based on the presenting signs and symptoms. In such cases, the diagnosis should be documented as the AE and not the individual sign/symptom. If a clear diagnosis cannot be established, each sign and symptom must be recorded individually. Once a diagnosis is made during evaluation or treatment, the investigator will update the AE record with this diagnosis by deleting the previous symptoms and entering the diagnosis. The rapid reporting of SAEs ensure that the sponsor shall have the necessary information to continuously assess the benefit-risk profile of the study drug in a clinical trial.

